## 7. Safety Analyses

## 7.1. Safety endpoints

- Frequency count and proportion of participants reporting immediate reaction occurring within 30 minutes of each vaccination.
- Frequency count and proportion of participants reporting solicited signs and symptoms occurring within 14 days of each vaccination.
- Frequency count and proportion of participants reporting unsolicited AEs occurring within 28 days of each vaccination.
- Frequency count and proportion of participants reporting SAEs occurring throughout the course of the study.

#### 7.2. Analysis of Safety endpoints

- The number and proportion of participants with at least one occurrence of an immediate reaction occurring within 30 minutes of each vaccination along with exact 95% CI of the proportion will be tabulated by study group. The severity, relationship to the vaccination, status at 30 minutes (ongoing or not), medication given (yes or no), reported as SAE (yes or no), and total number of the immediate reactions will be summarized by study group as well. Proportion of participants will be based on the number of participants who are in ITT analysis set or the safety analysis set when applicable. In addition, the immediate reaction will be listed at participant-level.
- The number and proportion of participants with at least one occurrence of local reactions (ecchymosis, erythema, edema, induration, and pain/tenderness) and with at least one occurrence of systemic reactions (fever, rash, cough, runny nose, change in eating habits, diarrhea, sleepiness, irritability, unusual crying, and vomiting) occurring greater than 30 minutes after receipt of each vaccination through 14 days post vaccination will be summarized by study group along with exact 95% CI of the proportion. Each specific local or systemic reaction will be summarized by severity for each study group. A listing including the local and systemic reactions at the participant-level will be provided as well.
- The number and proportion of participants with at least one unsolicited AE occurring within 28 days of each vaccination along with exact 95% CI of the proportion will be presented by study group. The AEs will be summarized by maximum severity and relationship to each vaccination for each study group. The total number, maximum severity, relationship to the vaccination, onset date, status/outcome, duration for resolved cases (resolution date onset date + 1), and medication given (yes or no) of AEs will be also summarized by study group. Summaries will be repeated for AEs found to be related to the vaccination. A listing of AEs at participant-level will be presented.
- The number and proportion of participants with at least one SAE occurring throughout the course of the study along with exact 95% CI of the proportion will be presented by study group. The SAEs will be summarized by maximum severity and relationship to each vaccination for each study group. The total number, maximum severity, relationship to the vaccination, onset date, status/outcome, duration for resolved cases (resolution date onset date + 1), and medication given

(yes or no) of SAEs will be also summarized by study group. Summaries will be repeated for SAEs found to be related to the vaccination. A listing of SAEs at participant-level will be presented.

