### **5.3.4. Reasons for Withdrawal**

After enrollment, a participant might be withdrawn from participation for several reasons:

- The investigator requests withdrawal of the participant because the child is not eligible or is no longer eligible, because he/she has developed an AE requiring withdrawal, or because the participant is non-compliant;
- A participant voluntarily withdraws at his/her own request;
- A participant is lost to follow-up;
- The trial is terminated prematurely by the sponsor, institutional or ethical review committees, or the regulatory agency; or
- Death of the participant.

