#### 2.3. Sample Size and Power

An enrollment size of 628 participants (314 per treatment group) was targeted to achieve an overall power of 90% (approximate individual power of 95% for each coprimary objective). This estimation is based upon a non-inferiority margin of 10% and a one-sided type-one error rate of 2.5% or less, and assumes (based on historical data) a 95% seropositivity rate for measles vaccine, a 90% seropositivity rate for rubella vaccine, and approximately 20% non-evaluable rate (exclusion for baseline seropositivity and loss to follow-up) at 56 days post-vaccination. The sample size calculations were based on the Farrington-Manning score test.

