#### 3.1. Analysis Set

All immunogenicity analyses and summaries will be performed on a per-protocol basis which will be considered as the primary approach to immunogenicity analyses. Supportive intention-to-treat immunogenicity analyses will also be conducted on all enrolled participants who received at least one dose of study vaccines and have at least one post-vaccination serology result. Safety analyses will be conducted on an intention-to-treat basis. In the event that there are participants who do not receive the vaccine(s) to which they were randomized, safety analyses will be performed on the safety analysis set as well. Analyses set definitions are provided below.

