#### 3.1.1. Intention-to-Treat Analysis Set

The Intention-To-Treat (ITT) set will include all participants who received a study vaccine. Participants in the ITT data set will be analyzed in the group to which participants have been assigned (not based on the actual vaccine received). Participants who withdraw or are terminated from the study will be included in the ITT data set until the time of withdrawal or termination. Participants in the ITT analysis set who have at least one post-vaccination serology result will be included in the supportive immunogenicity analysis.

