#### 3.1.2. Safety Analysis Set

The Safety Analysis Set (SAS) will include all participants who received a study vaccine and have at least one post-vaccination safety result. Participants in the safety data set will be analyzed based on the actual vaccine received rather than the group to which they have been randomized.

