## Measles Per-Protocol Analysis Set (measles-PP)

The measles-PP analysis set will be based on participants who meet all of the following criteria:

- Fulfilled the eligibility (inclusion/exclusion) criteria.
- Received all study vaccines as assigned.
- Provided a valid measles serology laboratory result at baseline and at 56 days postvaccination with MMR vaccine, with specimens taken within the windows indicated in Table 1.
- Did not take any prohibited concomitant medication within 28 days post-vaccination.
- Did not show seropositivity for measles at baseline.

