#### **3.3. Missing Data and Outliers**

#### 3.3.1. Missing Data

All descriptive statistics will be performed on subjects with available data. Nonmissing serology data are considered validated. Missing serology data are considered non-retrievable. Missing serology data will not be imputed and will be analyzed as if they were randomly missing.

If severity or relationship to a study vaccine for a reported adverse event (AE) or serious adverse event (SAE) is missing, an independent category "Missing" will be reported.

If start date associated with a reported concomitant medication, AE or SAE is incomplete or missing, the following rules will be applied:

- If the day of the date is missing, use the day of the date of vaccination if start month and year are the same as those of date of vaccination; otherwise use the 15th day of the month.
- If either month or year is missing, no imputations will be done.

If stop date for a concomitant medication, AE or SAE is incomplete or missing, the medication will be considered ongoing.

If date of withdrawal/study completion is completely missing, it will not be imputed.

If date of study vaccination is incomplete or missing, the following rules will be applied:

- If day is missing, use the day of the corresponding visit at which the vaccination is scheduled if start month and year are the same as those of date of the corresponding visit; otherwise use the 15th day of the month.
- If either month or year is missing, no imputation will be done.

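### Does SAP 7.2 understate later-dose immediate-reaction rates by naming the ITT or safety set as the denominator?

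*SAP*

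**What the plan says.** SAP 7.1 and 7.2 define immediate reactions by dose: the number and proportion of children with at least one reaction within 30 minutes of each vaccination, by study group, with an exact 95% CI. The denominator sentence in SAP 7.2 is: "Proportion of participants will be based on the number of participants who are in ITT analysis set or the safety analysis set when applicable". The solicited-reaction and unsolicited-AE paragraphs of SAP 7.2 name no denominator.

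Three other parts of the SAP bear on it.

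- SAP 3.1 makes ITT the basis for safety and adds the safety set conditionally: "In the event that there are participants who do not receive the vaccine(s) to which they were randomized".
- SAP 3.1.1 admits to ITT anyone given a study vaccine, with a time limit: "Participants who withdraw or are terminated from the study will be included in the ITT data set until the time of withdrawal or termination". SAP 3.1.2 has no such limit, but it says "Participants in the safety data set will be analyzed based on the actual vaccine received".
- SAP 3.3.1, within the general considerations for all analyses, says "All descriptive statistics will be performed on subjects with available data".

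Doses fall on Day 0 (both groups), Day 56 (CD-JEV, Group 2 only) and Day 84 (second MMR, both groups). SAP 3.4 reports numbers to one decimal place where applicable.

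**The concern.** The endpoint is per dose and the named sets are not. A child vaccinated only on Day 0 belongs to both sets, so a table for the Day 56 or Day 84 dose built literally on the set size would include children who were never at risk of reacting to that dose. The reported rate would then be too low.

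The plan does foresee missed or wrong doses. SAP 3.1 provides for them, and each per-protocol set separately requires "Received all study vaccines as assigned". Nor does a missed dose automatically end participation. Protocol 5.3.4 says "After enrollment, a participant might be withdrawn from participation for several reasons", Protocol 5.3.5 limits the grounds on which the investigator may withdraw a child, and Protocol 7.14 says no child is to be dropped solely for a visit outside its window.

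The dilution would also be uneven. Group 1 receives CD-JEV on Day 0, so for that vaccine only the separate-administration arm could be affected, and secondary objective 6 describes safety under concurrent and separate administration. For the second MMR dose both arms could be affected.

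**Working it through.** **1. The group size.** SAP 2.3 plans 314 per group. The Farrington-Manning sample size for rubella (90% in both arms, margin 10 points, one-sided 2.5%, power 95%) uses the constrained estimates 0.8313 and 0.9313 under the null:

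n = [(1.960 × √(0.8313×0.1687 + 0.9313×0.0687) + 1.645 × √(2×0.9×0.1)) / 0.10]² = 250.7, rounded up to 251.

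251 / 0.8 = 313.75, so 314. The plan's figure is reproduced and 314 is used below.

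**2. Which children are exposed to the problem.** Taking the SAP rules in turn:

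- Withdrawn or lost before the dose: Protocol 5.3.4 lists loss to follow-up as a withdrawal reason, and SAP 3.1.1 drops such children from ITT from that point.
- Still in the study but not given the dose: there is no 30-minute observation after that dose, hence no available data under SAP 3.3.1.
- Safety set, used only if some children did not receive their randomized vaccines: SAP 3.1.2 analyzes by vaccine actually received. This fixes the group and does not expressly set N for each dose, but SAP 3.3.1 still applies.

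Dilution therefore arises only if an analyst sets these rules aside in favor of a literal reading of SAP 7.2.

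**3. Size on the literal reading.** If a share d of the set did not receive the dose, reported rate = (rate among recipients) × (1 − d). The documents give no d, so 2%, 5% and 10% are assumptions. Event counts of 0 and 3 are also assumptions. Recipients = 314 × (1 − d), rounded. Intervals are Clopper-Pearson.

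| Denominator | d | 0 events: upper limit | 3 events: rate (95% CI) | 3 events, one decimal |
|---|---|---|---|---|
| 314 (literal) | – | 1.17% | 0.96% (0.20–2.77) | 1.0 (0.2–2.8) |
| 308 | 2% | 1.19% | 0.97% (0.20–2.82) | 1.0 (0.2–2.8) |
| 298 | 5% | 1.23% | 1.01% (0.21–2.91) | 1.0 (0.2–2.9) |
| 283 | 10% | 1.30% | 1.06% (0.22–3.07) | 1.1 (0.2–3.1) |
| 251 | 20% | 1.46% | 1.20% (0.25–3.45) | 1.2 (0.2–3.5) |

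At one decimal the zero-event upper limit prints as 1.2% on 314, 308 and 298, as 1.3% on 283 and as 1.5% on 251.

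**4. Why the 20% row is not a realistic ceiling for ITT.** It borrows the planning allowance, "approximately 20% non-evaluable rate (exclusion for baseline seropositivity and loss to follow-up) at 56 days post-vaccination". Children seropositive at baseline stay in the study and are due the later doses, so they are not missed doses. Children lost to follow-up leave ITT under SAP 3.1.1. What remains, children who stay in follow-up but miss a dose, is only a part that the documents do not size.

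**5. More frequent events.** With 6 reactors the literal rate is 1.91% (6/314), against 1.95%, 2.01% and 2.12% on 308, 298 and 283. With 15 it is 4.78%, against 4.87%, 5.03% and 5.30%. The largest of these gaps is 5.30 − 4.78 = 0.52 points, at 10% missed doses.

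**The case for a change.** The best case for a change is that a specific sentence normally overrides a general one. SAP 7.2 is the specific rule for this table, SAP 3.3.1 is a general missing-data rule, and a dose never given is not obviously missing data. The until-withdrawal limit in SAP 3.1.1 does not cover a child who stays in the study, and SAP 3.1.2 lacks it. If the sentence only chooses between two sets, then SAP 7.2 states no denominator per dose at all. SAP 4.2 does not list the number receiving each dose. The remedy would be cheap, because Protocol 5.3.3 already requires the vaccines given to each child to be documented. Were the same rule carried over to solicited reactions, commoner events would shift more: 85/283 = 30.0% would appear as 85/314 = 27.1% at 10% missed doses (both figures assumed).

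Much of this is fair as a comment on drafting. The passages are not reconciled, and showing N in each table would help a reader. It does not establish a biased result. The sentence follows the ITT-or-safety-set choice of SAP 3.1 and nowhere says that non-recipients count as reaction-free. A general rule need not be repeated in every later section to apply. The solicited and unsolicited paragraphs contain no conflicting sentence, so for them SAP 3.3.1 governs and the 30.0% against 27.1% example requires carrying over a rule that is not written there. The disposition gap is also narrower than it looks. SAP 4.2 tabulates visit completion and blood collection at each applicable visit, and Group 2's Day 56 and Day 84 doses are given at blood-draw visits. For Group 1's Day 84 dose, which has no blood draw, only visit completion helps. Participant-level listings of immediate reactions are planned as well.

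**Conclusion.** No change is called for. This is unclear wording that an analyst following the whole SAP would resolve sensibly, with the recipients of each dose as the denominator. If the rules in SAP 3.1.1 and 3.3.1 are applied dose by dose, or if no dose is missed, the effect is zero.

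On the literal reading, with 0 or 3 assumed events and 2% to 10% assumed missed doses, printed figures change by at most 0.1 percentage point. The one exception is the upper confidence limit for 3 events at 10%, which moves by 0.3 (2.8% to 3.1%). More frequent reactions or more missed doses would make the gap larger, in proportion to (1 − d), and the documents give neither quantity.

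The endpoint is a descriptive secondary one with no planned between-group test. Day 0 rates, which carry the concurrent-versus-MMR-alone comparison, and the co-primary non-inferiority analyses are untouched. No conclusion of the trial depends on the choice.

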##### **3.1.2. Secondary Objectives**

1. To demonstrate the non-inferiority of MMR vaccination in terms of mumps immunogenicity when administered to infants 9 months of age concomitantly with CD-JEV compared to administered alone, as assessed by the rate of seropositivity 56 days after vaccination.

Mumps vaccine immunogenicity will be evaluated by the presence of serum anti-mumps IgG antibody. Seropositivity will be defined as an OD ratio  $\geq 1.10$  using a commercial ELISA manufactured by Zeus Scientific, Inc., Branchburg, NJ

2. To evaluate serum anti-measles geometric mean neutralizing antibody concentration (GMC) and anti-rubella IgG GMC at 56 days post-vaccination, comparing when MMR vaccine is co-administered with CD-JEV to when MMR vaccine is given alone.
3. To evaluate anti-measles, anti-mumps, and anti-rubella seroconversion rates 56 days after vaccination, comparing when MMR vaccine is co-administered with CD-JEV to when MMR vaccine is given alone. For participants seronegative at baseline, seroconversion will be defined as a change

to seropositive status (as defined above). For participants seropositive for measles or rubella at baseline, seroconversion will be defined as a four-fold rise in concentration.

4. To compare the anti-JE seropositivity rate 28 days after CD-JEV vaccination administered concurrently with MMR vaccine to CD-JEV administered alone. Anti-JE seropositivity will be defined as an anti-JE serum neutralizing antibody titer of  $\geq 1:10$ , as measured by JE PRNT-50.
5. To describe anti-JE neutralizing antibody GMTs 28 days after CD-JEV vaccination when MMR vaccine is co-administered compared to when CD-JEV is administered alone.
6. To describe the safety profiles of CD-JEV and MMR vaccine when given concurrently and separately, as assessed by immediate reactions occurring within 30 minutes, solicited injection site and systemic adverse reactions occurring within 14 days, unsolicited adverse events (AEs) occurring within 28 days, and SAEs throughout the course of the study.

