## 4. STUDY DESIGN

This study will be a phase 4 open-label trial in which 628 Philippine infants 9 months of age will be randomized 1:1 to one of two arms:

- Group 1: 314 children receiving one dose of CD-JEV vaccine and one dose of MMR vaccine concurrently at enrollment; Group 1 will also receive a second dose of MMR per the routine immunization schedule at D84 (12 months of age).
- Group 2: 314 children receiving one dose of MMR vaccine at enrollment and one dose of CD-JEV 56 days later. Group 2 will receive a second dose of MMR per the routine immunization schedule at D84 (12 months of age).

Following receipt of study vaccine, infants will be monitored for immediate reactions during the first 30 minutes, solicited injection site and systemic adverse reactions for 14 days, unsolicited adverse events for 28 days, and serious adverse events throughout the duration of the study. All safety events will be identified or observed by study staff and/or reported by a parent. Solicited adverse reactions will be recorded by the parent on diary cards or assessed during clinic visits. Study staff will make a follow-up call to the participant's parent/guardian 2 days post vaccination (+3 days) to check on the welfare of the participant and ensure the diary card is being completed. The parent will return for a clinic visit 14 days post vaccination (+3 days) for the study staff to review the diary card, conduct safety evaluations, and review any adverse events. Information regarding unsolicited AEs will be collected during any scheduled or unscheduled clinic visit. Events will be graded for severity and assessed for relatedness to vaccination by the study clinician.

The study will be open-label; no placebo control will be employed. Due to the unequal number of injections per visit in each study arm, safety assessments will be unblinded.

Blood samples for serologic testing will be collected on Day 0, Day 28(+7), and Day 56(+7) for Group 1; and Day 0, Day 56(+7), Day 84(+7) for Group 2.

Baseline serologies will test for antibodies to JE, measles, mumps, rubella, and dengue virus. Antibody responses to CD-JEV will be tested 28(+7) days after vaccination, while antibody responses to the first dose of MMR will be tested 56(+7) days after vaccination. All laboratory testing will be conducted in a blinded fashion.

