## **6.2. Dosage, Preparation, and Administration of Study Vaccines**

The vaccines in general should be gently shaken prior to administration to assure homogenous suspension. CD-JEV will be administered subcutaneously into the anterolateral aspect of the right upper thigh. MMR vaccine will be administered subcutaneously into the anterolateral aspect of the left upper thigh.

CD-JEV will be supplied in 5-dose vials as a lyophilized powder that looks like a milky-white crisp cake. After reconstitution, it turns into a transparent orange-red liquid. Each 0.5 mL human dose for subcutaneous injection contains not less than 5.4 log PFU of live JE virus. A single dose of 0.5 mL should be administered by subcutaneous injection with the rest of the vial contents discarded.

Measles-mumps-rubella vaccine appears as a white to slightly pink dry cake. It will be supplied in its monodose commercial presentation. The vaccine should be reconstituted only with the diluent supplied (sterile water for injection). A single dose of 0.5 mL should be administered by subcutaneous injection.

Standard immunization practices will be observed and care will be taken to administer the injections. As with all injectable vaccines, appropriate medical treatment, staff, and supervision will be readily available in case of rare anaphylactic reactions following administration of the study vaccine and epinephrine 1:1000 will be available in case of any anaphylactic reactions.

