## 2.1.2. Secondary Objectives

1. To demonstrate the non-inferiority of MMR vaccination in terms of mumps immunogenicity when administered to infants 9 months of age concomitantly with CD-JEV compared to administration alone, as assessed by the rate of seropositivity 56 days after vaccination.

Mumps vaccine immunogenicity will be evaluated by the presence of serum antimumps IgG antibody. Seropositivity will be defined as an OD ratio  $\geq$ 1.10 using a commercial ELISA manufactured by Zeus Scientific, Inc., Branchburg, NJ.

- 2. To evaluate geometric mean concentration (GMC) for serum anti-measles neutralizing antibody concentration and anti-rubella IgG GMC at 56 days post-vaccination, comparing when MMR vaccine is co-administered with CD-JEV to when MMR vaccine is given alone.
- 3. To evaluate anti-measles, anti-mumps, and anti-rubella seroconversion rates 56 days after vaccination, comparing when MMR vaccine is co-administered with CD-JEV to when MMR vaccine is given alone. For participants seronegative at baseline, seroconversion will be defined as a change to seropositive status (as defined above). For participants seropositive for measles or rubella at baseline, seroconversion will be defined as a four-fold rise in concentration.
- 4. To compare the anti-JE seropositivity rate 28 days after CD-JEV vaccination administered concurrently with MMR vaccine to CD-JEV administered alone. Anti-JE seropositivity will be defined as an anti-JE serum neutralizing antibody titer of ≥1:10, as measured by JE PRNT-50.
- 5. To describe geometric mean titer (GMT) for anti-JE neutralizing antibody titer 28 days after CD-JEV vaccination when MMR vaccine is co-administered compared to when CD-JEV is administered alone.
- 6. To describe the safety profiles of CD-JEV and MMR vaccine when given concurrently and separately, as assessed by immediate reactions occurring within 30 minutes, solicited injection site and systemic adverse reactions occurring

within 14 days, unsolicited adverse events (AEs) occurring within 28 days, and SAEs throughout the course of the study.

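### SAP 7.2 does not split solicited local reactions by injection site, so Group 1 at Day 0 counts two thighs beside one in Group 2

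*SAP*

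**What the plan says.** Secondary objective 6 in Protocol 3.1.2, repeated in SAP 2.1.2, is: "To describe the safety profiles of CD-JEV and MMR vaccine when given concurrently and separately". Solicited injection-site reactions within 14 days are one of its components.

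SAP 7.2 sets the summary rule. The unit is the participant with "at least one occurrence of local reactions (ecchymosis, erythema, edema, induration, and pain/tenderness"), and these reactions, "occurring greater than 30 minutes after receipt of each vaccination through 14 days post vaccination will be summarized by study group", carry an exact 95% CI. It continues: "Each specific local or systemic reaction will be summarized by severity for each study group". It also plans that "A listing including the local and systemic reactions at the participant-level will be provided as well". Study group and severity are the only stated splits.

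The sites are fixed by vaccine. Protocol 6.2 states that "CD-JEV will be administered subcutaneously into the anterolateral aspect of the right upper thigh" and assigns MMR to the left thigh. Under Protocol 7.3, Group 1 has both injections at Day 0 and Group 2 has MMR only. Under Protocol 7.7.2, Group 2 has CD-JEV alone at Day 56. At Day 84 both groups have one injection, the second MMR dose.

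The documents acknowledge the imbalance once, as a reason for open assessment: "Due to the unequal number of injections per visit in each study arm, safety assessments will be unblinded" (Protocol 4, repeated in SAP 2.2). The analysis section does not return to it.

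**The concern.** The trial is meant to inform whether the two vaccines can be given at one visit, so readers will compare the Day 0 columns for local reactions. In Group 1 that column means a reaction at either of two sites. In Group 2 it means a reaction at the only site. An excess in Group 1 could come from the second needle, from a stronger reaction at a site because the vaccines were given together, or from both. The planned table cannot tell these apart.

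Causality grading does not help, because Protocol 9.2.3 treats every solicited local sign in the 14-day window as related to vaccination. Severity has a smaller version of the same gap. If an infant has grade 1 redness on one thigh and grade 2 on the other, SAP 7.2 does not say which grade is tabulated; it states a maximum-severity rule for unsolicited AEs and SAEs but not for solicited reactions.

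The design already contains the remedy: each vaccine always goes in the same thigh, so recording the side identifies the vaccine.

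**Working it through.** **Inputs.** From the documents: two sites in Group 1 at Day 0, one in Group 2 at Day 0 and one at Day 56 (Protocol 6.2, 7.3, 7.7.2), and 314 infants per group (SAP 2.3). Neither document gives a per-site local-reaction rate, so there is no figure of the plan's own to reproduce. The rates below are assumptions.

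**Formula.** Let pM and pJ be the probabilities of a local reaction at the MMR and CD-JEV sites, the same whether the vaccines are given together or apart (no true effect of co-administration). Group 2 at Day 0 then shows pM. Group 1 at Day 0 shows:

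- full overlap between sites: max(pM, pJ)
- independent sites: 1 − (1 − pM)(1 − pJ)
- never both in the same child: pM + pJ

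The artefact in the Day 0 comparison is this figure minus pM, that is, the probability that the CD-JEV site reacts and the MMR site does not.

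**Equal site rates.**

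| Assumed rate per site | Full overlap | Independent | Never together | Group 2 Day 0 | Artefact (points) |
|---|---|---|---|---|---|
| 5% | 5% | 1 − 0.95² = 9.8% | 10% | 5% | 0 to 5 |
| 10% | 10% | 1 − 0.90² = 19% | 20% | 10% | 0 to 10 |
| 20% | 20% | 1 − 0.80² = 36% | 40% | 20% | 0 to 20 |
| 30% | 30% | 1 − 0.70² = 51% | 60% | 30% | 0 to 30 |

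An intermediate case is a within-infant correlation of 0.5. The any-site rate is 2p − [p² + 0.5p(1 − p)]. At p = 10% this is 0.20 − (0.01 + 0.045) = 14.5%. At p = 20% it is 0.40 − (0.04 + 0.08) = 28%.

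**Unequal site rates.** With MMR 10%, CD-JEV 2% and independence, Group 1 shows 1 − 0.90 × 0.98 = 11.8%, an artefact of 1.8 points. With MMR 5%, CD-JEV 10% and full overlap, it shows 10% against 5%.

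**How it would look at the planned size.** In the 10% independent case, 60/314 in Group 1 has an exact 95% CI of 14.9% to 23.9%, and 31/314 in Group 2 has 6.8% to 13.7%. The intervals do not overlap, although nothing has changed at either site.

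**Separability.** Under independence, an MMR site at 20% with CD-JEV at 10%, and the reverse, both give 1 − 0.80 × 0.90 = 28%. The pooled figure cannot show which site is responsible.

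**By thigh.** With 10% at each site and no true effect, left/MMR reads 10% vs 10% (Group 1 Day 0 vs Group 2 Day 0) and right/CD-JEV reads 10% vs 10% (Group 1 Day 0 vs Group 2 Day 56). The artefact is zero whatever the overlap.

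**The case against.** The safety objective is descriptive. Neither Protocol 11.5.2 nor SAP 7.2 plans a between-group safety test, difference or margin, and the total local burden of a two-injection visit is a legitimate description of concurrent use. This stands. What is at stake is a misreading of a table, not an error in a planned inference.

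The wording may also already allow a split. SAP 7.2 refers to each vaccination and Protocol 9.1 to each study vaccine, which could mean each injection. Against that, Protocol 7.14, Table 3, treats the Day 0 pair as a single MMR/CD-JEV vaccination, and SAP 7.2 gives no rule for assigning a reaction to a vaccine. The text is ambiguous, and the per-vaccine reading is not made operational.

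The side may well be captured. Local signs are defined at the injection site and graded partly by limb segment (Protocol 8.1.3 and 9.2.3.1), and a participant-level listing is planned. The diary card, eCRF and table shells are not part of the two documents, so absence of site data cannot be claimed. A listing, however, is not a tabulated proportion with a CI, and it is not said to carry the side.

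Finally, a by-thigh table does not make the CD-JEV comparison clean. Group 2 infants at Day 56 are about 8 weeks older than at Day 0 and have already had MMR. They are also those still attending, and their parents have already kept one diary. SAP 3.2 itself considers age before CD-JEV as a covariate for the GMT comparison. This also stands: only the left-thigh Day 0 comparison is both concurrent and randomised.

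**Conclusion.** The gap is real and limited. Neither document specifies a local-reaction summary by injection site or vaccine, so the Group 1 Day 0 figure mixes the number of injections with any effect of giving the vaccines together. The local reactogenicity of each vaccine under co-administration is not separable in the planned tables.

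A reader might infer that objective 6 cannot be answered for either vaccine. The documents do not support that. Group 2 describes MMR alone at Day 0 and CD-JEV alone at Day 56, so the separate-administration half is covered for both. Concurrent use is still described for the regimen as a whole. The immediate, systemic, unsolicited and SAE components are unaffected. The imbalance is also confined to Day 0: each group receives three injections over the study.

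The size depends on rates the documents do not give. At an assumed 10% per site with no true effect, the artefact is 0 to 10 points (9 if the sites are independent). For equal site rates it disappears only if reactions always coincide in the same infants. A large spurious excess is therefore possible but not assured. The change is worth making because it costs little and uses the fixed left/right assignment.

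**What to change.** In SAP 7.2, state that solicited local reactions are tabulated by injection site/vaccine and dose, with exact 95% CI and severity. Name the two comparisons:

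- Left thigh, MMR first dose: Group 1 Day 0 beside Group 2 Day 0 (concurrent and randomised).
- Right thigh, CD-JEV: Group 1 Day 0 beside Group 2 Day 56, with a footnote that Group 2 infants are then about 8 weeks older and have previously received MMR.

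Keep any-site as an additional row, labelled at Day 0 as two injections versus one. Confirm that the diary card and eCRF record left and right thigh separately, and add the field if they do not.

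The cost is SAP wording, a few more table rows and possibly one data field. No visits or infants are added.
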